9.6. Selection and Timing of Doses

Subjects will be assigned to treatment arms (see Section 9.3) and are planned to receive their assigned treatment as outlined in Section 9.1.

9.6.1. Special Treatment Considerations

9.6.1.1. Premedication for Infusions

Premedication for the infusions is not planned. However, if an infusion reaction occurs, appropriate medication may be used as determined by the study investigators (see Section 9.9).

Any premedication given will be documented as a concomitant therapy (see Section 9.9).

9.6.1.2. Management of Infusion Reactions

Because of the risk of an infusion reaction with any biological agent, all subjects should be monitored for 1 hour after dosing or longer according to local standard of care. Symptoms and signs that may occur as part of an infusion reaction include but are not limited to fever, chill, nausea, headache, bronchospasm, hypotension, angioedema, throat irritation, rash, pruritus,

myalgia, and/or dizziness. In the event that a significant infusion reaction occurs, the following guidance should be followed:

- the investigational product infusion should be slowed or stopped, depending on the symptoms or signs present
 - if slowed or stopped, the infusion may be continued in accordance with signs and symptoms at the investigator's discretion
- supportive care should be employed in accordance with the symptoms or signs

9.7. Continued Access to Investigational Product

LY3074828 will not be made available to subjects after conclusion of the study.

9.8. Blinding

This is a double-blind study; to preserve the blinding of the study, a minimum number of Lilly personnel will see the randomization table and treatment assignments before the study is complete. A study site pharmacist or other trained person will be unblinded at the site for investigational product preparation.

Emergency unblinding for AEs may be performed through the IWRS, which may supplement or take the place of emergency codes generated by a computer drug-labeling system. This option should be used ONLY if the subject's well-being requires knowledge of the subject's treatment assignment. All notifications resulting in an unblinding event are recorded and reported by the IWRS.

If an investigator, a member of site personnel performing assessments, or a subject is unblinded to a subject's treatment, that subject must be discontinued from the study. In cases in which there are ethical reasons to have the subject remain in the study, the investigator must obtain specific approval from a Lilly clinical research physician for the subject to continue in the study.

In case of an emergency, the investigator has the sole responsibility for determining if unblinding of a subject's treatment assignment is warranted. Subject safety must always be the first consideration in making such a determination. If a subject's treatment assignment is unblinded, Lilly must be notified immediately.

Nonresponder subjects entering the extension period will receive study drug in an unblinded fashion.

9.9. Concomitant Therapy

All concomitant medication taken during the study must be recorded on the concomitant medication case report form (CRF).

All subjects should maintain their usual medication regimens for concomitant conditions or diseases throughout the study unless those medications are specifically excluded in the protocol.

Subjects taking concomitant medications should be on stable dosages at the time of baseline and should remain at stable dosages throughout the study unless changes need to be made because of AEs. Additional systemic drugs are to be avoided during the study, unless required to treat AEs. Other medications may be allowed if they are approved by the sponsor or its designee.

Uses of nonlive (inactivated) vaccinations are allowed for all subjects. Use of live, attenuated vaccines is prohibited. Chronic use of nonsteroidal anti-inflammatory drugs during the study is excluded. Chronic use of opioid drugs during the study is excluded. Occasional use of acetaminophen in over-the-counter dose ranges for headache, menstrual pain, or other transient conditions is acceptable but should be held on study visit days until after assessments have been completed, as much as possible; use of prophylactic daily aspirin (up to 162.5 mg) is permitted.

Concomitant therapies for treatment of UC during the study are permitted only as outlined in [Table AMAC.3](#).

Table AMAC.3. Permitted Medications for Treatment of Ulcerative Colitis

Drug Class	Conditions for Use
Oral 5-ASA or sulfasalazine	Subjects were receiving the medications at baseline and the prescribed dose was stable for at least 2 weeks before screening endoscopy. Dosages should remain stable throughout the study unless the medication is discontinued because of toxicity. If stopped, the medication should not be restarted during the study.
Azathioprine or 6-mercaptopurine	Subjects were receiving the medications at baseline and the prescribed dose was stable for at least 8 weeks before baseline. Dosages should remain stable throughout the study unless the medication is discontinued because of toxicity. If stopped, the medication should not be restarted during the study.
Oral corticosteroid therapy (prednisone at a stable dosage \leq 20 mg/d or equivalent oral steroid)	
Oral steroids are allowed during the study up to 20 mg/d of prednisone or equivalent, providing that the prescribed dose has not been changed within 2 weeks of screening endoscopy. Decrease of the steroid dosage due to tapering regimen is allowed during the study per investigator judgment, except during the induction period. If the steroid tapering is commenced, the daily dose of prednisone or equivalent is recommended to be decreased by 2.5 mg every week until dose 0.
 
 • Equivalent of oral budesonide is up to 9 mg/d and must be stable within 2 weeks of endoscopy. Decrease of the steroid dosage due to tapering regimen is allowed during the study per investigator judgment, except during the induction period. If the steroid tapering is commenced, is recommended to be decreased 3mg every week until dose 0. • Equivalent for oral beclomethasone is up to 5 mg/d and must be stable within 2 weeks of endoscopy 
Dosages should remain stable throughout the study unless the medication is discontinued because of toxicity. If stopped, the medication should not be restarted during the study.

Abbreviation: 5-ASA = 5-aminosalicylic acid.

9.10. Treatment Compliance

Every attempt will be made to select subjects who have the ability to understand and comply with study instructions. The investigator is responsible for discussing methods to ensure high treatment compliance with the subject before randomization.

All doses of study medication will be administered at the study site. Deviation(s) from the prescribed dosage regimen should be recorded in the CRF.

If a subject is noncompliant with study procedures and/or investigational product administration, the investigator should assess the subject to determine the reason for noncompliance and educate and/or manage the subject as appropriate to improve compliance. If, in consultation with Lilly or its designee, the noncompliance is deemed to be significant or if further noncompliance occurs, the subject should be discontinued from the study. A subject will be considered significantly

noncompliant if he or she fails to attend for administration of study medication within the required treatment window as defined in the study schedules ([Attachment 1](#) and [Attachment 2](#)).

10. Efficacy, Health Outcome/Quality of Life Measures, Safety Evaluations, Sample Collection and Testing, and Appropriateness of Measurements

Study procedures and their timing (including tolerance limits for timing) are summarized in the study schedules ([Attachment 1](#) and [Attachment 2](#)). A list of the specific planned laboratory tests to be performed for this study is provided in [Attachment 3](#).

10.1. Efficacy Measures

10.1.1. Primary Efficacy Measure

The primary efficacy endpoint is clinical remission at Week 12. Clinical remission is defined as having achieved the following Mayo subscores at Week 12: a rectal bleeding subscore of 0, stool frequency subscore of 0 or 1 (with 1 point decrease from baseline), and endoscopy subscore of 0 or 1.

10.1.2. Secondary Efficacy Measures

Secondary efficacy endpoints are clinical response at Week 12 and endoscopic remission at Week 12 and Week 52. Clinical response is defined as having achieved at Week 12 a decrease in 9-point Mayo subscore (rectal bleeding, stool frequency, and endoscopy) inclusive of ≥ 2 points and $\geq 35\%$ from baseline with either a decrease of rectal bleeding subscore of ≥ 1 or a rectal bleeding subscore of 0 or 1. Endoscopic remission is defined as having achieved a Mayo endoscopic subscore of 0.

10.1.3. Subject Diary

Subjects will be provided with a diary tool during screening in order to record information such as:

- number of stools per day
- presence of blood in the stools (if any)

Diary data will be assessed at the clinic, at each visit defined in the study schedule. Diary information will be used to calculate the subject's Mayo score. Data will include information collected over 3 days prior to each study visit. Three days of subject diary data must exclude data from days when bowel preparation or endoscopic exam (flexible proctosigmoidoscopy/colonoscopy) occur and exclude data from the day after the endoscopic exam.

Subjects should enter diary data continuously throughout the study.

The study data completion guidelines and study data management plan will provide detailed information on use of patient-reported outcome (PRO) measures and the subject diary.

10.1.4. Endoscopy/Histopathology

To ensure quality data and standardization, endoscopy will be performed locally at clinical sites per the study schedules ([Attachment 1](#) and [Attachment 2](#)) and using the same endoscopist throughout the trial wherever possible.

Endoscopy images will be obtained during each endoscopy and will be sent for independent central reading and determination of the Mayo endoscopy subscore. A detailed image review charter from the central reading laboratory will outline the endoscopic procedures, video recordings, and equipment to be used for video capture and transmission of endoscopic recordings. For each subject, video recording of the entire endoscopic procedure will be performed using a storage medium provided by the sponsor or designee. The endoscopic recordings will be read centrally in a blinded manner by a qualified gastroenterologist according to the image review charter. The Mayo score used for clinical endpoints in the trial will use the Mayo endoscopy subscore derived from the central reader.

To ensure quality data and standardization, colonic tissue histopathologic scoring will be performed by the central reading laboratory. A detailed image review charter from the central reading laboratory will outline the histopathologic procedures to be used for secure specimen transfer, processing, slide preparation, and digitization of slides for histopathologic scoring. The histologic images will be read centrally in a blinded manner by a qualified pathologist according to the image review charter.

10.2. Health Outcome/Quality of Life Measures

The self-reported questionnaires will be administered according to the study schedule in countries where the questionnaires have been translated into the native language of the region and linguistically validated. The health outcome measures in this trial will be the PGI-S, PGI-I, IBDQ, and the SF-36.

PGI-S: The PGI-S is a 1-item subject-rated questionnaire designed to assess the subject's impression of their disease symptoms at baseline (Guy 1976; Yalcin and Bump 2003). Responses are graded on a 7-point scale in which a score of 1 indicates that the subject's symptom(s) are "normal," a score of 2 indicates that the subject feels "borderline ill," a score of 3 indicates that the subject feels "mildly ill," a score of 4 indicates that the subject(s) feel "moderately ill," and scores of 5, 6, and 7 indicate that the subject feels "markedly ill," "severely ill," and "extremely ill," respectively.

PGI-I: The PGI-I scale is a subject-rated instrument designed to assess the subject's impression of change in their symptom(s) (Guy 1976; Yalcin and Bump 2003). Responses are graded on a 7-point Likert scale in which a score of 1 indicates that the subject's symptom(s) is "very much better," a score of 4 indicates that the subject's symptom(s) has experienced "no change," and a score of 7 indicates that the subject's symptom(s) is "very much worse."

IBDQ: The IBDQ is a 32-item subject-completed questionnaire that measures 4 aspects of subjects' lives: symptoms directly related to the primary bowel disturbance, systemic symptoms, emotional function, and social function (Guyatt et al. 1989). Responses are graded on a 7-point

Likert scale in which 7 denotes “not a problem at all” and 1 denotes “a very severe problem.” Scores range from 32 to 224; a higher score indicates a better quality of life.

SF-36: The SF-36 is a 36-item subject-completed measure designed to be a short, multipurpose assessment of health in the areas of physical functioning, role-physical, role-emotional, bodily pain, vitality, social functioning, mental health, and general health (Ware and Sherbourne 1992; Ware et al. 1993; McHorney et al. 1994). The 2 overarching domains of mental well-being and physical well-being are captured by the mental and physical component summary scores. Responses are graded on Likert scales of varying lengths/points. The summary scores range from 0 to 100; higher scores indicate better levels of function and/or better health.

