6.1. General Considerations

Eli Lilly and Co. will be responsible for conducting the statistical analysis and for the generation, validation and final production of the Efficacy and Health Outcomes tables, figures and listings (TFLs) proposed in this document. Robarts Clinical Trials, a clinical research organization, will be responsible for conducting the statistical analysis and for the generation, validation and final production of all other tables, figures and listings (TFLs) proposed in this document.

Any change to the data analysis methods described in the protocol will require an amendment ONLY if it changes a principal feature of the protocol. Any other change to the data analysis methods described in the protocol and the justification for making the change will be described in the clinical study report. Additional exploratory analyses of the data will be conducted as deemed appropriate.

Continuous data will be summarized in terms of the number of observations, mean, standard deviation (SD), median, minimum, and maximum. The minimum and maximum will be reported to the same number of decimal places as the raw data recorded in the database. The mean and median will be reported to one more decimal place than the raw data recorded in the database. The SD will be reported to two more decimal places than the raw data recorded in the database. In general, the maximum number of decimal places reported shall be four for any summary statistic.

Categorical data will be summarized in terms of the number of patients providing data at the relevant time point (n), frequency counts and percentages. Percentages will be presented to one decimal place. Percentages will be calculated using n (the number of observations with non-missing values) as the denominator.

Change from baseline will be calculated as the visit value of interest minus the baseline value. If all baseline values are missing for a particular variable, then the change from baseline and percent change (or percent improvement) from baseline will not be calculated.

All confidence intervals (CIs) and statistical tests will be two-sided unless otherwise specified. P-values which are greater than or equal to 0.001, and less than or equal to 0.999, will be presented to three decimal places. All other p-values which are less than 0.001 will be presented as '<0.001', while p-values greater than 0.999 will be presented as '>0.999'. CIs will be presented to one more decimal place than the raw data.

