6.2. Analysis Populations

The patient populations to be analyzed for this study are defined in the table presented below:

Table 2 Analysis Populations

Population	Definition
Screening	All patients who signed informed consent and participated in the screening period (Visit 1). This population will be used for the presentation of patient disposition.
Intent-to-Treat (ITT) Population	Efficacy and health outcome analyses will be conducted on the intent-to-treat population (ITT). The ITT population is defined as all randomized patients, even if the patient does not take the assigned treatment, does not receive the correct treatment, or otherwise does not follow the protocol. Patients will be analyzed according to the treatment to which they were assigned.
Safety Population	Safety analyses will be conducted on the Safety Population, defined as all randomized patients who receive at least one dose of study treatment. Patients will be analyzed according to the treatment to which they were assigned.

Induction Responders	A subset of the ITT population and will include those patients who are re-randomized to one of the two maintenance dosing period LY arms.
All enrolled in Extension Period	A subset of the ITT population and will include only the patients who participated in the Extension Period.

Analyses of the maintenance dosing period and the extension periods will be based on the corresponding enrolled population as described in the table above.

The Schedule of Events outlined in the protocol (attachment 1) specifies the allowable windows for assessments. A sensitivity analysis of the primary analysis may be conducted to investigate the exclusion of patients /assessments deemed to be major deviations from the protocol.

A Per-Protocol population may be evaluated in this study and patients to be excluded from that population will be identified through protocol deviations. All protocol exemptions and violations will be listed as described in section 9.10 of the protocol.

All statistical analyses will be performed using SAS software Version 9.2 (or a higher version). Visualizations tools such as Spotfire may also be used for dynamic displays.

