6.4.1. Non-Responder Imputation (NRI)

The primary outcome is the proportion of patients with clinical remission at 12 weeks. For this and other categorical efficacy endpoints (for example, clinical remission (week 52), clinical response (week 12, 52), and endoscopic remission (week 12, 52)), non-responder imputation (NRI) will be used for missing clinical assessment values. Specifically, all patients who discontinue from the study at any time prior to week 12 for any reason or fail to have an adequate week 12 efficacy assessment will be considered a non-responder at week 12. Patients who discontinue from the study for any reason at any time prior to week 52 after having enrolled into the Maintenance Period or fail to have an adequate week 52 efficacy assessment, will be considered a non-responder at week 52.

The NRI may be applied at any time point specified for analysis.

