6.4.2. Last Observation Carried Forward

An LOCF analysis will be performed on PGI-I.

This is both a sensitivity analysis, and an analysis for regulatory agencies that prefer this approach. This approach is identical to the mBOCF approach, with one exception: for patients discontinuing investigational product due to an AE, the last non-missing post-baseline observation before discontinuation will be carried forward to the corresponding endpoint for evaluation. Randomized patients without at least one post-baseline observation will not be included for evaluation.

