6.12. Health Outcomes/Quality-of-Life Analyses

6.12.1. Secondary Health Outcomes Endpoints

There are four self-administered questionnaires used for measuring health outcome in this trial:

1. PGI-S (Patient’s Global Impressions of Severity score)
2. PGI-I (Patient’s Global Impressions of Improvement score)
3. IBDQ (Inflammatory Bowel Disease Questionnaire score)
4. SF36 (36-Item Short Form Health Survey score)

Where appropriate, the total scores and sub-totals for individual dimensions collected will be summarized with means and 95% CIs by time point and by treatment group. The summary table will also include the change from baseline scores wherever applicable. The mean raw scores and mean change from baseline scores with corresponding 95% CIs will be presented graphically by treatment group and in a longitudinal fashion.

The ITT population will be used for all health outcome analyses

Mean change from baseline will be summarized by treatment group.

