6.12.1.1. SF36 (36-Item Short Form Health Survey score)

Summaries of domain and summary scores will be provided by visit and change from baseline to postbaseline visits.

An ANCOVA model will be used to analyze the change from baseline in the physical component score (PCS) and the mental component score (MCS) through Week 24. The ANCOVA model will include treatment, geographic region, and prior biologic experience (prior biologic experience vs prior biologic naïve), and baseline value (consistent with adjustments of other efficacy analysis) as fixed effects and baseline score as a covariate with change from baseline as the dependent variable. To test the treatment difference between LY3074828 and placebo, the LS mean difference, 95% CI, and p-value will be presented. The LOCF approach will be used to impute missing data.

Analyses will be repeated for the eight health domains (physical functioning, bodily pain, role limitations due to physical problems, role limitations due to emotional problems, general health perceptions, mental health, social function, and vitality).

Summary statistics per treatment group will be tabulated for the transformed scale scores (physical functioning, role limitations / physical health, bodily pain, general health perceptions, vitality, social functioning, role limitations / emotional, mental health) and the two summary scores (PCS and MCS).

Minimum Clinically Important Differences (MCID):

The summary and analyses of the SF-36v2 Acute Score will include the number of patients achieving a MCID, which is defined for each summary score, physical component score (PCS) and the mental component score (MCS), as:

- MCID \geq at least 2.5 or 5-point improvement (decrease) in PCS
- MCID \geq at least 2.5 or 5-point improvement (decrease) in MCS.

The proportion of patients achieving the SF-36v2 score MCID will also be analyzed using a logistic regression model with treatment, geographic region, and prior biologic experience (prior biologic experience vs prior biologic naïve), and visit (when appropriate) as fixed effects. The p-value and 95% CI of the odds ratio from the logistic regression model will be reported. The 95% CI of the MCID rate difference will be calculated using the Newcombe-Wilson method without continuity correction. The NRI method described in Section 6.4.1 will be used to impute missing data.

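### The SF-36 MCID responder analysis has no rule for patients in countries where the questionnaire is not offered, and as written it counts them as non-responders

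*Protocol*

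**What the plan says.** Protocol section 10.2 makes administration of the PGI-S, PGI-I, IBDQ and SF-36 conditional: they are given "in countries where the questionnaires have been translated into the native language of the region and linguistically validated".

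The SAP sets the analysis rules:

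- **Population.** Section 6.12.1: "The ITT population will be used for all health outcome analyses". Section 6.2 defines ITT as "all randomized patients, even if the patient does not take the assigned treatment". Neither section makes an exception for a questionnaire that was not offered.
- **Responder analysis.** Section 6.12.1.1 analyses the proportion reaching the SF-36 MCID by logistic regression, and states: "The NRI method described in Section 6.4.1 will be used to impute missing data".
- **NRI rule.** Under section 6.4.1, patients who leave the study before Week 12 or who "fail to have an adequate week 12 efficacy assessment will be considered a non-responder at week 12". Week 52 has a parallel rule.
- **Continuous SF-36 scores.** For the ANCOVA of the physical and mental component scores, section 6.12.1.1 says: "The LOCF approach will be used to impute missing data". The LOCF rule in section 6.4.2 adds: "Randomized patients without at least one post-baseline observation will not be included for evaluation".
- **Percentages in general.** Section 6.1: "Percentages will be calculated using n (the number of observations with non-missing values) as the denominator".

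**The concern.** NRI is a sensible convention when a patient drops out or misses a visit, because the absence may itself reflect treatment failure. It has no such basis for a patient who could never have been asked. Country is fixed before randomization, so the absence carries no information about treatment.

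The protocol provides for such patients, and the SAP does not separate a questionnaire that was not administered from one that was missed. If any participating country lacks a validated version, the reported MCID rates would reflect translation coverage as well as drug effect. The two SF-36 analyses in the same SAP section would also rest on different patients for no stated reason.

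**Working it through.** **1. The plan's own figure.** The only design calculation in the documents concerns Week 12 clinical remission: 30% against 7.5%, 60 per arm, two-sided 0.05, 89% power (protocol 12.1, SAP 5.2). The pooled chi-square approximation is

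power = Φ{ [ |p₁ − p₂| − 1.96·√(2p̄(1 − p̄)/n) ] / √( [p₁(1 − p₁) + p₂(1 − p₂)]/n ) }

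With p̄ = 0.1875 and n = 60 this is Φ{(0.225 − 0.1397)/0.0682} = 89.4%, so the stated figure reproduces. It is unaffected by this point. The documents give no design figure for the SF-36 MCID.

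**2. What the rules do to a patient never asked.** The patient is randomized and therefore in ITT. There is no Week 12 SF-36, so section 6.4.1 assigns non-response and the patient enters the logistic regression as a failure. In the ANCOVA the same patient has no post-baseline value to carry forward, and no baseline from which to form a change, so drops out.

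**3. Effect on the rates.** Let f be the share never asked, equal across arms in expectation because country precedes randomization. A true rate p among patients who could be asked becomes p(1 − f). The difference becomes (p₁ − p₂)(1 − f).

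**4. Illustration.** These inputs are assumptions absent from the documents: MCID rates of 55% and 30%, and f of 5%, 10% and 20%. The 60 per arm is the plan's figure. Under NRI the formula uses n = 60 with rates p(1 − f). Restricting to patients who could be asked uses n = 60(1 − f) with rates p, and keeps the difference at 25.0 points and the odds ratio at 2.85.

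| f | Rates under NRI | Difference (points) | Odds ratio | Power, NRI | Power, restricted | Power lost to NRI (points) |
|---|---|---|---|---|---|---|
| 0 | 55.0% vs 30.0% | 25.0 | 2.85 | 79.9% | 79.9% | 0 |
| 5% | 52.3% vs 28.5% | 23.8 | 2.75 | 76.2% | 77.8% | 1.6 |
| 10% | 49.5% vs 27.0% | 22.5 | 2.65 | 72.3% | 75.5% | 3.2 |
| 20% | 44.0% vs 24.0% | 20.0 | 2.49 | 64.1% | 70.4% | 6.3 |

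Worked line for f = 20%: under NRI, p̄ = 0.34 and power = Φ{(0.200 − 0.1695)/0.0845} = 64.1%. Restricted to 48 per arm, p̄ = 0.425 and power = Φ{(0.250 − 0.1978)/0.0976} = 70.4%.

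**5. Chance imbalance.** SAP section 6.5 says that randomization is not stratified by country, so the numbers never asked can differ between arms by chance. With a true rate of 40% in both arms and 6 against 12 of 60 never asked, NRI gives 0.40 × 54/60 = 36% against 0.40 × 48/60 = 32%. The region covariate (North America, Japan, Rest of World) would not fully remove this, because availability can differ between countries within Rest of World.

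**The case against.** **The group may be empty.** Section 10.2 states a condition and does not say that any participating country fails it. Attachment 1 schedules the questionnaires with no country exemption. The protocol leaves detailed use of patient-reported measures to data completion guidelines and a data management plan that are not among these documents. This stands: the documents support a gap in the rules and do not show that patients are in fact miscounted.

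**The general rules might already exclude these patients.** Section 6.1 uses non-missing values as the denominator for percentages and computes no change without a baseline. The wording of section 6.4.1 could also be read as covering only planned assessments that were missed. These readings are possible but do not settle the matter. The denominator rule is general, the MCID paragraph calls specifically for imputation, and an imputed value is no longer missing.

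**The loss is modest and conservative.** This stands in large part. A reader might attribute the whole fall from 80% to 64% power at f = 20% to NRI. Most of it comes from having no data on those patients, since the restricted analysis also falls, to 70%. A reader might also infer bias towards one arm, but country precedes randomization, so the expected effect is dilution in every arm.

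**Missing baseline is a different matter.** One might infer that every patient without a baseline SF-36 is imputed as a failure and should likewise be excluded. The documents do not support that. A patient with a Week 12 SF-36 and no baseline does not plainly meet either trigger in section 6.4.1. In a country where the SF-36 is offered, a missing baseline is ordinary missing data, and keeping such a patient in ITT is a defensible choice.

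**Conclusion.** The point holds in a limited form. The protocol allows for patients who are never given the SF-36. SAP sections 6.12.1, 6.12.1.1 and 6.4.1, read together, would count them as MCID non-responders, while the SF-36 ANCOVA would leave them out.

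The size depends on f, which is unknown: nil if every participating country has a validated version, and otherwise a proportional shrinkage of both rates and their difference. The figures of 2, 3 and 6 power points rest on assumed MCID rates and on f of 5%, 10% and 20%.

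The reach is narrow. It is one responder analysis of one secondary questionnaire, without multiplicity control. The SAP specifies no NRI-based responder analysis for the PGI-S, PGI-I or IBDQ, and the primary endpoint is untouched.

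**What to change.** In SAP section 6.12.1.1, define the MCID analysis set as ITT patients in countries or languages where the SF-36 was available. Apply NRI only within that set, and report by arm how many patients were not administered the questionnaire. Availability is fixed before randomization, so the randomized comparison is preserved, and the set agrees with the ANCOVA in leaving out patients who were never asked. Patients in covered countries whose baseline SF-36 is missing should not be excluded on that ground as part of this change.

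The cost is a sentence or two in the SAP, one country/language flag in the analysis data, and a slightly smaller denominator if anyone is affected. No new data are needed. If every country has a validated version, the result does not change.
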